7.3 Secondary Efficacy Endpoint

[figure not shown]
The analysis methods for the secondary endpoints are summarized in the table below.

Secondary Endpoints	Analysis Methods	Missing Data Handling
Change of NMPP measured by NRS from Baseline to Week 12 and 24	Following same steps in Section 7.2.2 for the primary endpoint	
	ANCOVA (as used for the primary endpoint)	MI approach (as used for the primary endpoint)
CFB in the monthly mean Endometriosis Daily Impact Pain Scale for DYS, NMPP and DYSP at Week 12 and 24	Following same steps in Section 7.2.2 for the primary endpoint	
	ANCOVA (as used for the primary endpoint)	MI approach (as used for the primary endpoint)
Change of DYS measured by NRS from Baseline to Week 24	Following same steps in Section 7.2.2 for the primary endpoint	
	ANCOVA (as used for the primary endpoint)	MI approach (as used for the primary endpoint)
Change of DYSP measured NRS from Baseline to Week 12 and 24	Following same steps in Section 7.2.2 for the primary endpoint	
	ANCOVA (as used for the primary endpoint)	MI approach (as used for the primary endpoint)
CFB by visit in permitted rescue medication use	The number of medication and the percentage of days that permitted rescue medication is used will be summarized as two separate endpoints	Missing data will not be imputed
	Analysis of variance (ANOVA)	
Change in menstrual period heaviness (bleeding) from Baseline by visit	The changes of mean scores of heaviness (bleeding) in the menstrual cycle collected from eCOA.	Missing data will not be imputed

[figure not shown]
7.3.1 CFB in DYS Measured by NRS at Week 24

The Measurement of Week 24: because the Week 24 (EOS) visit may or may not occur during menstruation, the measurement of Week 24 will be defined by the following 2 approaches, depending on the scenarios. The objective of these approaches is to capture a complete menstrual cycle and designate it as the EOS menstrual cycle.

- If EOS visit occurs during menstruation, the EOS menstrual cycle is defined as the interval that begins from the first day of the previous menstruation to the day before the first day of the menstruation during which the EOS visit occurred.

- If EOS visit occurs outside of a menstruation period, the latest menstruation period prior to the EOS visit will be identified. The EOS menstrual cycle will begin at the end of the menstruation period immediately before the latest menstruation period to the end of the latest menstruation period.

The main analytical approach in Section 7.2.2 will be applied for this analysis.

In addition, sensitivity analysis for primary endpoint defined in section 7.2.3 will be applied for this analysis as well.

7.3.2 CFB in NMPP Measured by NRS at Week 12 and Week 24

The Baseline, Week 12 and Week 24 measurements will follow the definitions in sections of 7.2.1 and 7.3.1 for the time window, respectively.

The mean CFB and %CFB in NMPP at Week 12 and Week 24 will be summarized for each treatment group with point estimates (least square mean [LSM]), the associated standard errors [SEs]) and 95% CIs. Estimated treatment differences (compared for each HMI-115 treatment group against the placebo group) along with corresponding 95% CIs will be presented using the ANCOVA model with treatment group, region as the fixed effects and baseline NMPP as a continuous covariate.

The main analytical approach in Section 7.2.2 will be applied for this analysis.

In addition, sensitivity analysis for primary endpoint defined in section 7.2.3 will be applied for this secondary endpoint as well.

NMPP measured by NRS will be summarized by treatment and visit using observed values.

A by-subject listing will be presented for NMPP.

7.3.3 CFB in DYSP Measured by NRS at Week 12 and Week 24

For DYSP Measured by NRS, the Week 12 and Week 24 measurements will follow the definitions in sections of 7.2.1 and 7.3.1 for the time window, respectively.

The main analytical approach in Section 7.2.2 will be applied for this analysis.

In addition, sensitivity analysis for primary endpoint defined in section 7.2.3 will be applied for this secondary endpoint as well.

The mean CFB and %CFB in DYSP measured by NRS will be summarized by treatment and visit using observed values.

A by-subject listing will be presented for DYSP.

7.3.4 CFB in the Monthly (every menstruation cycle) Mean Endometriosis Daily Impact Pain Scale for DYS, NMPP and DYSP at Week 12 and Week 24

Endometriosis Daily Impact Pain Scale will be used to record the mean change every month from Baseline to Week 12 measurement and Week 24 measurement. For DYS, NMPP and DYSP, responses of "None," "Mild," "Moderate," and "Severe" will be assigned a score of 0, 1, 2, and 3, respectively. For DYSP, the choice of "Not Applicable" applies to subjects not sexually active for reasons other than endometriosis pain. Responses of "Not Applicable" for the assessment of DYSP will be treated as missing values and will not be included in the summaries/analyses.

The average pain scores for DYS, NMPP and DYSP for Week 12 and Week 24 will follow the definitions in sections of 7.2.1 and 7.3.1 for the time window.

The main analytical approach in Section 7.2.2 will be applied for this analysis.

In addition, sensitivity analysis for primary endpoint defined in section 7.2.3 will be applied for this secondary endpoint as well.

Endometriosis Daily Impact Pain Scale for DYS, NMPP and DYSP will be listed.

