9.4.5 Secondary Efficacy Endpoints

Efficacy

The analysis methods for the secondary endpoints are summarized in the table below. Details of model specifications and sample SAS codes will be presented in the SAP.

Measurement of Week 24: Because the Week 24 (EOS) visit may or may not occur during menstruation, the measurement of Week 24 will be defined by the following 2 approaches, depending on the scenarios. The objective of these approaches is to capture a complete menstrual cycle and designate it as the *EOS menstrual cycle*.

- If EOS visit occurs during menstruation, the *EOS menstrual cycle* is defined as the interval that begins from the first day of the previous menstruation to the day before the first day of the menstruation during which the EOS visit occurred.
- If EOS visit occurs outside of a menstruation period, the *latest* menstruation period prior to the EOS visit will be identified. The *EOS menstrual cycle* will begin at the end of the menstruation period *immediately before* the latest menstruation period to the end of the latest menstruation period.

Secondary Endpoints	Analysis Methods
Change of NMPP measured by NRS from	ANCOVA and MMRM methods as used for
Baseline to Week 12 and 24	the primary endpoint.
CFB in the monthly mean Endometriosis	ANCOVA and MMRM methods as used for
Daily Impact Pain Scale for DYS, NMPP and	the primary endpoint.
DYSP at Week 12 and 24	
Change of DYS measured by NRS from	ANCOVA and MMRM methods as used for
Baseline to Week 24	the primary endpoint.
Change of DYSP measured NRS from	ANCOVA and MMRM methods as used for
Baseline to Week 12 and 24	the primary endpoint.
CFB by visit in permitted rescue medication	The number of medication and the percentage
use	of days that permitted rescue medication is
	used will be summarized as two separate
	endpoints. Depending on the frequency of use

Version 6.0 66 of 138 April 11, 2024

Secondary Endpoints	Analysis Methods
	of permitted rescue medications, treatment comparison may be compared using an ANOVA with treatment and region as the main effects. The correlation between the use of rescue medications and the DYS and NMPP NRS will be explored by summary statistics and graphical presentations.

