7.3.5 CFB by Visit in Permitted Rescue Medication Use

Permitted rescue medication will be provided to subjects from Visit 2 for rescue use if needed for endometriosis associated pain throughout the study. Use of analgesic medication will be reported by subjects in the e-Diary on a daily basis from Visit 2 through the Follow-up period.

The average pill count of permitted rescue medications along with CFB will be summarized by visit measurement including Baseline, Week 6, Week 12 and Week 24 (following the definitions in sections of 7.2.1 and 7.3.1 for the time window). The percentage of days with analgesic rescue use which will be calculated based on those days in the visit window with non-missing data will be summarized by visit.

In addition, the pill count of rescue medications at Week 12 separated by Tier 1 and Tier 2 (following the definitions in sections of 7.2.1 for the time window) as the dependent variable, treatment comparison may be compared using an ANCOVA model with treatment and region as the main effects and baseline of pill count as a continuous covariate.

The correlation between the use of rescue medications (in terms of pill count) and DYS and NMPP measured by NRS at Week 12 measurement will be explored by summary statistics including Pearson and Spearman correlation coefficients and graphical presentation (e.g., scatter plot).

Daily use of permitted rescue medications will be listed.

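### Rescue medication use: the SAP 7.3 table names an ANOVA, while SAP 7.3.5 adds an optional baseline-adjusted ANCOVA for Week 12 pill count only, so percentage of days has no baseline-adjusted comparison

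*SAP*

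**What the plan says.** The endpoint is "CFB by visit in permitted rescue medication use". In the SAP 7.3 table its row covers two measures: "The number of medication and the percentage of days that permitted rescue medication is used will be summarized as two separate endpoints". The method cell reads "Analysis of variance (ANOVA"), with no model terms and no visit singled out.

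Protocol 9.4.5 covers the same two measures ("The number of medication and the percentage" of days). It allows an ANOVA with treatment and region as main effects, names no baseline term, and makes the comparison depend on how often rescue medication is used.

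SAP 7.3.5, the detailed text for the endpoint, has three parts:

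- Average pill count and its change are summarised at Baseline and Weeks 6, 12 and 24.
- Percentage of days is summarised by visit: "The percentage of days with analgesic rescue use which will be calculated based on those days in the visit window with non-missing data". No between-arm model is named for it.
- A model is then added: "In addition, the pill count of rescue medications at Week 12 separated by Tier 1 and Tier 2" is the dependent variable, and "treatment comparison may be compared using an ANCOVA model with treatment and region as the main effects", with baseline pill count as a continuous covariate.

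SAP section 10, which lists changes from the protocol, does not mention a move from ANOVA to ANCOVA for this endpoint.

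**The concern.** A reader preparing the tables finds two models for the Week 12 pill count and no statement of which one is reported. For percentage of days the only between-arm model is the one in the table, and on the protocol's terms it does not adjust for baseline.

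This is out of line with the rest of the SAP. The four other rows of the 7.3 table that name a model (NMPP, the Daily Impact Pain Scale, DYS at Week 24, DYSP) all use the baseline-adjusted ANCOVA of the primary analysis, and EHP-5 in SAP 9.4 also gets an ANCOVA. PGIC in SAP 9.3 gets an ANOVA, but PGIC has no baseline value. Rescue use is recorded daily from Visit 2, so its baseline is available.

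At stake are some precision on a secondary endpoint, and a choice between models that could be made after the results are known.

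**Working it through.** **1. Scope of the two models**

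| | SAP 7.3 table | SAP 7.3.5 model |
|---|---|---|
| Method | ANOVA | ANCOVA |
| Terms | none listed (Protocol 9.4.5: treatment, region) | treatment, region, baseline pill count |
| Measures | number of medications; percentage of days | pill count, by tier |
| Visits | by visit | Week 12 |
| Status | method cell only (Protocol 9.4.5: optional, depends on frequency of use) | optional, introduced as an addition |

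The overlap is the Week 12 pill count. Percentage of days, and Weeks 6 and 24 for both measures, have no baseline-adjusted model.

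**2. The plan's own figure**

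No sizing figure is given for rescue use. The only one is for DYS NRS: 34 per group, SD 2.0, two-sided 0.05, 80% power. Exact noncentral-t power is 80.8% for a 1-point within-group change (paired t) and 81.2% for a 1.4-point between-group difference (two-sample t). Both reproduce. The figure is used below only to set n = 34 per arm.

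**3. Precision of ANCOVA against ANOVA on change**

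Assume equal variance s² at baseline and follow-up, with correlation r between them. The documents give no r for rescue use, so a range is shown.

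- Variance of the change: 2(1−r)s².
- Residual variance after regressing on baseline: (1−r²)s².
- Ratio: (1−r²) / [2(1−r)] = (1+r)/2. The SE ratio is its square root.

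If ANOVA on change has 80% power at 34 per arm (normal approximation), the standardised difference is (1.960 + 0.842) × √(2/34) = 0.679. ANCOVA power is then Φ(2.802/√[(1+r)/2] − 1.960).

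| r | Variance ratio | SE ratio | Equivalent n per arm (34 ÷ ratio) | ANCOVA power |
|---|---|---|---|---|
| 0.3 | 0.65 | 0.81 | 52.3 | 93.5% |
| 0.5 | 0.75 | 0.87 | 45.3 | 89.9% |
| 0.7 | 0.85 | 0.92 | 40.0 | 86.0% |
| 0.9 | 0.95 | 0.97 | 35.8 | 82.0% |

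If the ANOVA were run on the follow-up value instead of the change, the SE ratio would be √(1−r²): 0.95, 0.87 and 0.71 at r = 0.3, 0.5 and 0.7.

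**4. How often the two models disagree**

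Simulation of four arms of 34 with normal data and no region term, 4,000 runs per setting, one active arm against placebo:

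| r | Type I error, ANOVA / ANCOVA | Disagree on p<0.05, no effect | Disagree on p<0.05, real effect |
|---|---|---|---|
| 0.3 | 4.6% / 4.7% | 5.4% | 15.8% |
| 0.5 | 4.9% / 5.0% | 4.6% | 13.8% |
| 0.7 | 4.6% / 4.4% | 3.4% | 9.6% |

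Both models hold the 5% level. The real-effect column uses an effect for which ANOVA on change has about 80% power.

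**The case against.** The strongest reply is that the two passages are compatible. The 7.3.5 model is presented as an addition, and it is confined to one visit and to counts split by tier. SAP 7.2.1 says the tiers cannot be converted into each other, so a per-tier Week 12 model can sit beside a broader ANOVA. Much of this stands. It confines any direct overlap to the Week 12 pill count, but it does not say which result is reported there, and it leaves percentage of days without adjustment.

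Four stronger readings are tempting, and the documents do not support them.

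- *ANOVA is the SAP's default and the whole endpoint has two conflicting answers.* Neither document names a default. Both the protocol's ANOVA and the 7.3.5 ANCOVA are worded as optional, and their scopes differ.
- *The ANOVA is biased.* Under randomisation both models estimate the same effect, and an ANOVA on change already subtracts baseline. It does so less efficiently and leaves some chance imbalance through regression to the mean.
- *The primary result is exposed.* The composite rule in SAP 7.2.1 and 7.2.2 classifies each woman by her own change in rescue use or tier. It does not use the between-arm rescue model.
- *Baseline use is known to vary widely.* The documents give no distribution of rescue use.

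It is also fair to say that the protocol made its test depend on frequency of use for a reason. Opioid use may be sparse, and with many zero counts the formulas above may not describe the actual gain.

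**Conclusion.** The point holds as a minor one, and acting on it is a free improvement. The SAP table and SAP 7.3.5 should agree on one model. At present they overlap for the Week 12 pill count, and percentage of days has no baseline-adjusted comparison.

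The size is a standard error about 8% to 19% smaller with ANCOVA than with ANOVA on change (ratio 0.92 to 0.81) for r between 0.7 and 0.3. This assumes equal variances, roughly normal data, and a correlation that the documents do not give. The simulated disagreement of 9.6% to 15.8% under a real effect rests on the same assumptions. The primary analysis is not affected.

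The absence of a baseline term in the table's ANOVA is inferred from Protocol 9.4.5, version 6.0. The SAP cites version 6.1, which is not among the documents, so that wording should be checked. The near-identical sentence structure in Protocol 9.4.5 and SAP 7.3.5 suggests that 7.3.5 was updated and the table was not, but this too is inference.

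**What to change.** 1. In the SAP 7.3 table, replace ANOVA for this row with ANCOVA: treatment, region, and baseline of the same measure.
2. In SAP 7.3.5, apply that model to pill count and to percentage of days at Weeks 6, 12 and 24, with Week 12 named as the main comparison.
3. State whether the modelled pill count is the total or is split by tier. SAP 7.2.1 defines an average count over NSAIDs and/or opioids and also says that the tiers are not convertible.
4. Change *may be* to *will be*. If the team wants an exception for sparse use, write the condition down in advance.
5. Record the departure from Protocol 9.4.5 in SAP section 10.

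The cost is a few lines of text and a small set of models on data already derived: 2 measures × 3 visits = 6 models if pill count is a total, or 3 × 3 = 9 if it is split into two tiers. The trial has no multiplicity adjustment, so naming Week 12 as the main comparison keeps the added models from widening the choice of result. No new data collection is needed.

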7.2 Primary Efficacy Endpoint

7.2.1 Definition of Endpoint

[figure not shown]
The primary efficacy endpoint is the mean change of DYS measured by NRS from Baseline to Week 12 measurement. The NRS for overall endometriosis-associated pain ranges from 0 (no pain) to 10 (severe pain). Higher scores mean a worse outcome.

- The Baseline measurement will be derived from the last complete menstruation cycle (menstruation period should be ≥ 2 days) during the Screening Period prior to Day 1. It will be designated as the baseline menstrual cycle and is defined as following:

[figure not shown]
- If the first administration of IMP occurs within the menstruation but not the last day of the menstruation, the baseline menstrual cycle is defined as the interval that first day of the previous menstruation to the day before the menstruation during which the first administration of IMP occurs.

- If the first administration of IMP occurs on the last day of the menstruation, the baseline menstrual cycle is defined as the interval that begins from the first day after the end of the previous menstruation to the first dosing day.

[figure not shown]

- If the first administration of IMP does not occur during the menstruation, the baseline menstrual cycle is defined as the last menstruation period before the first dose plus the non-menstrual period prior to the last menstruation.

[figure not shown]

- The Week 6 measurement will be from a complete menstrual cycle (menstruation period should be ≥ 2 days) prior to Week 7.

[figure not shown]
- If Week 7 visit occurs during menstruation, the menstrual cycle is defined as the interval that begins from the first day after the end of the previous menstruation to the last day of the menstruation during Week 7 visit occurred. It is expected that the end of this menstruation may be days after the Week 7 visit.

- If Week 7 visit occurs outside of a menstruation period, the closest menstruation period to Week 7 visit will be identified. This menstrual period may be before or after the Week 7 visit. In either case, the menstrual cycle will begin at the end of the menstruation period immediately before the closest menstruation period to the last day of the closest menstruation period.

[figure not shown]

Or

[figure not shown]

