- The Week 12 measurement: Because the Week 12 (EOT) visit may or may not occur during menstruation, the measurement of Week 12 will be defined by the following 2 approaches, depending on the scenarios. The objective of these approaches is to capture a complete menstrual cycle (menstruation period should be ≥ 2 days) and designate it as the EOT menstrual cycle.

[figure not shown]
- If EOT visit occurs during menstruation, the EOT menstrual cycle is defined as the interval that begins from the first day after the end of the previous menstruation to the last day of the menstruation during which the EOT visit occurred. It is expected that the end of this menstruation may be days after the EOT visit.

- If EOT visit occurs outside of a menstruation period, the closest menstruation period to the EOT visit will be identified. This menstrual period may be before or after the EOT visit. In either case, the EOT menstrual cycle will begin at the end of the menstruation period immediately before the closest menstruation period to the last day of the closest menstruation period.

Or

The average score is calculated by adding up the daily DYS measured by NRS during analysis window and dividing by the actual number of days with non-missing daily DYS data.

The **primary estimand** is described by the following attributes:

Treatment conditions of interest:	HMI-115 at 60,120 and 240 mg vs. placebo. Placebo treatment is the control group.
Subject population:	Women with moderate to severe endometriosis-associated pain and have surgical diagnosis
Endpoint:	Mean change (change from baseline) in DYS measured by NRS at Week 12 measurement
Population-level summary:	Differences between each HMI-115 treatment group compared with placebo in mean change (change from baseline) in DYS measured by NRS at Week 12, including least square mean (LSM) with its associated standard error (SE) and 95% CIs by using ANCOVA
Intercurrent events (ICEs) and strategies to handle ICEs:	
Premature withdrawal from study treatment due to any reasons (Hypothetical strategy)
 
At least 15% increase in average pill count of rescue analgesic medications(endometriosis-associated) compared to Baseline. (Composite strategy)

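### The Week 24 cycle in SAP 7.3.1 lacks the two-day minimum menstruation set for Baseline, Week 6 and Week 12, so a single day can become a subject's whole Week 24 DYS score

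*SAP*

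**What the plan says.** SAP 7.2.1 sets a minimum length of menstruation at three measurement points:

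- Baseline: "The Baseline measurement will be derived from the last complete menstruation cycle (menstruation period should be ≥ 2 days".
- Week 6: "The Week 6 measurement will be from a complete menstrual cycle (menstruation period should be ≥ 2 days) prior to Week 7".
- Week 12: the aim is to "capture a complete menstrual cycle (menstruation period should be ≥ 2 days) and designate it as the EOT menstrual cycle".

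SAP 7.3.1 uses almost the same sentence for Week 24, but without the minimum and without a reference back to it: "The objective of these approaches is to capture a complete menstrual cycle and designate it as the EOS menstrual cycle". It then gives two branches:

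- EOS visit outside menstruation: "the latest menstruation period prior to the EOS visit will be identified", and "The EOS menstrual cycle will begin at the end of the menstruation period immediately before the latest menstruation period". The window closes when that latest menstruation ends.
- EOS visit during menstruation: the window "begins from the first day of the previous menstruation to the day before the first day of the menstruation during which the EOS visit occurred".

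The DYS score (SAP 7.2.1) is the sum of the daily values divided by the number of days that have a value. No minimum number of days is set. SAP 7.3.2 to 7.3.5 use the 7.3.1 window for the Week 24 NMPP, DYSP, daily impact scale and rescue measures as well. Protocol 9.4.4 and 9.4.5 have no two-day rule at any time point, so the SAP introduced it for three of its four measurements.

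**The concern.** A change from baseline is easiest to interpret when both ends are measured by the same rule. Here the Baseline menstruation must last at least two days, while the Week 24 menstruation may last one. Nothing in the SAP says that the difference is intended.

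Week 24 DYS is the first secondary efficacy variable listed in SAP 1.3.1.2 and serves the persistence-of-efficacy objective in SAP 1.2.2. A programmer who follows 7.3.1 as written would accept a one-day menstruation as the latest one. For that subject, a persistence measure meant to average over a menses would rest on one diary entry, although scores from a fuller menses shortly before had been collected.

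**Working it through.** The plan states no figure that bears on this point, so the check compares the texts and then applies the SAP's averaging rule.

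**1. Which menses is scored**

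| EOS visit | Menses in the window | When the score rests on one day |
|---|---|---|
| Outside menstruation | The latest before the visit, of any length | The latest menses lasted one day |
| During menstruation | The previous one; the current one is excluded | The previous menses lasted one day |

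In the first branch the window opens at the end of the preceding menses, so that menses drops out. The wording does not settle whether its last day counts; if it does, the score rests on two days from two different menses.

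**2. The averaging rule on an illustrative subject** (assumed scores, not trial data; rescue rule not triggered)

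- Baseline menses 4, 7, 8, 6, 3: 28/5 = 5.6.
- Latest menses before EOS is one day scored 2: 2/1 = 2.0. Change = 2.0 − 5.6 = −3.6.
- Same, with a boundary day scored 3 counted: (3 + 2)/2 = 2.5. Change = −3.1.
- Two-day condition applied, falling back to the preceding menses 4, 6, 7, 5, 3: 25/5 = 5.0. Change = 5.0 − 5.6 = −0.6.
- One day scored 8 instead (the worst baseline day): 8/1 = 8.0. Change = 8.0 − 5.6 = +2.4.

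The last line shows that the rule itself fixes no direction. The result follows whatever that one day happened to be.

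**3. Noise in an affected score**

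Assume equal daily variances and a common correlation ρ between days of one menses. The variance of a k-day mean, relative to a single day, is (1 + (k − 1)ρ)/k.

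| ρ (assumed) | k = 1 | k = 2 | k = 5 |
|---|---|---|---|
| 0.3 | 1.00 | 1.3/2 = 0.65 | 2.2/5 = 0.44 |
| 0.5 | 1.00 | 1.5/2 = 0.75 | 3.0/5 = 0.60 |
| 0.7 | 1.00 | 1.7/2 = 0.85 | 3.8/5 = 0.76 |

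A one-day score therefore has 1/0.76 = 1.3 to 1/0.44 = 2.3 times the variance of a five-day mean. This applies only to women whose scored menses lasted one day, and the documents do not say how many there would be.

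**4. The other Week 24 measures**

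In the first branch the window runs from one menses to the next. It is shortened only if the one-day menses comes early. In that case the NMPP, DYSP, impact-scale and rescue averages also use fewer days. If the one-day menses comes at the usual interval, the non-menstrual part of the window is intact.

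**The case against.** The strongest reply is that this is a drafting slip in a secondary endpoint of a proof-of-concept trial. SAP 7.3.1 repeats the 7.2.1 sentence about a complete cycle, so the two-day meaning may have been meant to carry over, and a figure not shown may display it. Without the rule, Week 24 also agrees with the protocol. This is a fair reading of intent. But the SAP states the condition afresh at each of the other three points, so its absence at the fourth leaves the derivation open.

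Several limits stand:

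- A day of bleeding is not necessarily a menstruation. The diary asks about the period (Protocol 8.1.4) separately from uterine bleeding, which includes spotting (Protocol 8.1.5). The SAP does not say which answer defines menstruation.
- The two-day rule governs the length of menstruation, not the number of scored days. A missed entry can still leave one scored day at Baseline or Week 12.
- Short menses would be partly visible elsewhere: the period-length summaries in SAP 4.3 and 7.3.6 and the by-subject DYS listing in 7.2.2. These displays do not change the score.

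A reader might go further and infer that one-day menses are light and little painful, so that Week 24 looks too favourable. The documents say nothing about pain on such days. A reader might also put a number on it: an assumed 2 to 10% of women with a gap of 2 to 3 points gives 0.02 × 2 = 0.04 to 0.10 × 3 = 0.30 points in an arm mean. Neither input has a source, and an equal shift in every arm would cancel in the comparison with placebo. Nor does the menstrual event of special interest in Protocol 10.3.1 show an arm difference: it concerns 56 days without bleeding or spotting, not short menses.

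**Conclusion.** The inconsistency is in the text and the concern holds in limited form. As written, SAP 7.3.1 can rest a subject's Week 24 DYS score on one day and set it against a Baseline cycle that had to meet a stricter rule. This arises directly when the EOS visit is outside menstruation, and otherwise only when the previous menses lasted one day.

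The supported consequence is extra noise in the affected Week 24 scores (1.3 to 2.3 times the variance of a five-day mean, under assumed correlations of 0.7 to 0.3) and a change from baseline between differently defined cycles. The effect on the arm means cannot be sized from the documents, and neither a direction of bias nor a treatment-arm imbalance is supported. The Week 12 primary analysis is untouched. This is a cheap improvement to a secondary endpoint, not a threat to the trial's main conclusion.

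**What to change.** In SAP 7.3.1, attach to the Week 24 cycle the same two-day condition that 7.2.1 attaches to the other three. Then state the fallback: if the menstruation that would be scored is shorter than two days, use the latest earlier qualifying menstruation within the follow-up period; if there is none, Week 24 is missing and goes to the planned multiple imputation. It would also help to state which diary answer defines a menstruation day, and to consider a minimum number of non-missing DYS days at every time point.

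The cost is a few sentences and some derivation code. The length check exists for Week 12, but the fallback is new, because 7.2.1 does not say what happens when a menses fails the condition. There is a small statistical price: the fallback cycle lies somewhat closer to the last dose, a genuinely short menses is passed over, and a few scores become missing. Showing the result under the current definition as a sensitivity analysis covers this. If the data are already unblinded, keep the current definition and report the two-day version as a documented sensitivity analysis. If the difference from Week 12 is deliberate, the SAP should say why.
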